3. DRUG DESCRIPTION

Generic Name: naltrexone hydrochloride and bupropion hydrochloride extended-release tablet

Trade Name: MYSIMBA®/Contrave®

Indications for Use:

Mysimba/Contrave is indicated as an adjunct to a reduced-calorie diet and increased physical activity for chronic weight management in adults with an initial body mass index (BMI) of:

1. 30 kg/m² or greater (obese) or

2. 27 kg/m² or greater (overweight) in the presence of at least one weight-related comorbidity (e.g., hypertension, type 2 diabetes mellitus, or dyslipidemia).

Limitations of Use:

- 1. The effect of Mysimba/Contrave on cardiovascular morbidity and mortality has not been established.
- 2. The safety and effectiveness of Mysimba/Contrave in combination with other products intended for weight loss, including prescription drugs, over-the-counter drugs, and herbal preparations, have not been established.

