7. RATIONALE AND BACKGROUND

According to the World Health Organisation, weight-related health issues are some of the most significant global public health challenges. Worldwide obesity has nearly tripled since 1975. Obesity (body mass index [BMI] ≥30 kg/m2) and being overweight (BMI ≥27 kg/m2 to <30 kg/m2) are linked to psychosocial conditions and are major risk factors for chronic diseases, including cardiovascular disease, orthopaedic/degenerative joint disease, and diabetes. Globally there are more people who are obese than underweight and this occurs in every region except parts of sub-Saharan Africa and Asia. The World Health Organisation estimates that the prevalence of obesity and overweight, among adult men and women in Europe, is over 20% and over 50%, respectively. The major health risks and complications associated with obesity negatively affect quality of life and reduce average life expectancy. In addition to burdening the health care system, the treatment of overweight and obesity is a public health imperative. Long-term lifestyle changes are essential to mitigate obesity-related morbidity and mortality; however, for overweight and obese individual's lifestyle changes alone are insufficient, and pharmacotherapy should be considered and added.

Mysimba/Contrave, a fixed-dose combination of naltrexone (an opioid receptor antagonist) and bupropion (a selective neuronal re-uptake inhibitor of noradrenaline and dopamine), was approved in Europe for the treatment of adults with a BMI of \geq 30 kg/m2 (obese) or \geq 27 kg/m2 to <30 kg/m2 (overweight) in the presence of one or more weight-related co-morbidities (e.g., type 2 diabetes, dyslipidaemia, or controlled hypertension).

The European Medicines Agency (EMA) requested that Orexigen Therapeutics Ireland Limited (Orexigen) provide additional information on the utilisation of Mysimba in Europe and further

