9.3. Variables

9.3.1. Exposure

Exposure to Mysimba/Contrave will be identified through medication prescription or dispensing data (i.e., prescription or dispensing date, dosage [where available], and duration [where available]). The first Mysimba/Contrave prescription after 365 days with no prescription will be the index date, as depicted in Figure 1. All prescriptions of Mysimba/Contrave (or the two component products dispensed within 15 days) during the 548 days (18 months) following the index date will be captured. Patients will be assessed during the entire 548 days following the index date.

Figure 1. Index date, Exclusion and Covariate Assessment, and Follow-up Time for Study

Index Date (First prescription of Mysimba) Day 0

- a. Data are 'acceptable for research' for the patient and practice, coverage with computerized records throughout time period with no gaps
- b. Baseline conditions included: BMI, height, most recent weight, weight-related comorbidities (e.g., diabetes, dyslipidaemia), neuropsychiatric conditions (mania, bipolar disorder, major depressive disorder [MDD], anorexia nervosa, bulimia), hypertension, end-stage renal disease, seizure disorder, hepatic impairment (defined by Child-Pugh score category), central nervous system tumour, substance use/abuse including acute opiate withdrawal,;uncontrolled hypertension, seizures, bipolar disorder, MDD, anorexia nervosa, or bulimia; use of: naltrexone, bupropion, opioid or opiate agonist, or MAOI; pregnancy, or breastfeeding
- c. Earliest of: death, disenrollment, 548 days of follow-up, end of the study period

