9.3.2. Outcomes

When available, the following variables will be collected after initiation of Mysimba/Contrave (Post-Index Date). A draft listing of variables available in each country is included in Appendix 3 and will be included as final in the Statistical Analysis Plan (SAP).

Proprietary and Confidential:

This document cannot be used, distributed, or reproduced in any way without the prior written consent of Currax Pharmaceuticals LLC.

- 1. BMI, height, and weight prior to index date, the date of initiation of the medication(s) of interest, (obtained directly from data sources; BMI may be calculated if height and weight available). In the event that BMI and/or weight are not available through licensed access to the Scandinavian National Patient Registries, an attempt will be made to identify the obese population through diagnosis codes or procedures such as counseling for weight loss. It should be noted that this approach may identify a more obese and more motivated population than what would be identified on the basis of BMI. In addition, an approach may be implemented to predict BMI or apply published algorithms predicting BMI. Details will be laid out in the SAP.
- 2. Weight will be obtained if available 16-24 weeks post-index date to evaluate use inconsistent with labelled indication. BMI after index date will be obtained in the same timeframe, if available.
- 3. Relevant comorbidities (obtained via ICD-10 codes):
 - 1. Weight-related comorbidities (i.e., type 2 diabetes, dyslipidaemia, hypertension)
 - 2. Neuropsychiatric conditions (mania, bipolar disorder, major depressive disorder [MDD], anorexia nervosa, bulimia)
 - 3. Uncontrolled hypertension
 - 4. Moderate or severe renal impairment
 - 5. End-stage renal disease
 - 6. Seizure disorder
 - 7. Hepatic impairment (defined by Child-Pugh score category)
 - 8. Central nervous system tumour
- 4. Concomitant medication use, including: naltrexone, bupropion, CYP2B6 inhibitors, CYP2B6 inducers, CYP2B6 substrates, CYP2D6 substrates, drugs that lower seizure threshold, opioid or opiate agonist, or MAOI (obtained via ATC [outpatient, Nordic data] or NDC [US data])
- 5. Pregnancy status and breastfeeding status (obtained via ICD-10 codes)
- 6. AESIs (obtained via ICD-10 codes):
 - 1. Seizures

- 2. Suicidality (i.e., suicidal ideation, attempted suicide or completed suicide)
- 3. Neuropsychiatric events (i.e., mania or depression)
- 4. Hepatotoxicity
- 5. Severe hypersensitivity reaction

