- 6. Serotonin syndrome
- 7. Major adverse cardiovascular events (i.e., cardiovascular-related death, non-fatal myocardial infarction, or non-fatal stroke)

Deaths will also be described by treatment group, for those with vital status available.

- 7. Treatment discontinuation (assessed using ATC [outpatient, Nordic data] or NDC [US data])
- 8. Reason(s) for treatment discontinuation (obtained via ICD-10 codes in the 90 days prior to discontinuation)

All variables will be identified from the data sources via a pre-specified list of definitions (i.e., code lists; see Appendix 2). Occurrence of AESI based on diagnostic codes will be summarized for all patients, and for a subgroup of patients who do not adhere to conditions of the EU SmPC for the Scandinavian countries (adapted to local SmPC as needed) or to the FDA SmPC for the US. Such criteria include: not meeting appropriate criteria for the indication [obese (BMI \geq 30 kg/m²), or being overweight (BMI \geq 27 kg/m² to < 30 kg/m²) and having at least one weight-related co-morbidity (e.g., type 2 diabetes, controlled hypertension, or dyslipidemia) based on diagnostic codes. If BMI is not available, diagnostic and procedure codes for obesity and weight loss will be applied, recognizing that it will likely produce a more obese population than would be identified by BMI. Subgroup analyses will also be conducted to assess continuous treatment in patients with either renal or hepatic impairment.

Initiation of specific medications that could result with the occurrence of an event corresponding to an AESI (e.g., newly initiating anti-epileptic/seizure medication, newly initiating medications indicated for mania or depression) will also be tabulated. For hepatotoxicity, liver function tests can be used (when available) in addition to diagnostic codes.

For reason(s) patients who discontinue treatment (i.e., do not refill their prescription), events (potential AESIs and contraindications) and clinical status (magnitude of weight loss or gain)

Proprietary and Confidential:

occurring within the 90-day window prior to discontinuation will be summarized. It should be noted that weight may not be available in the Scandinavian registries.

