9.3.3. Covariates

When available, the following variables needed to conduct analysis for the primary and secondary research objectives will be collected. Variable availability from each country will be summarized in the SAP and is included in Appendix 3 in draft form.

Demographics and Baseline variables (Within 365 days before index date unless otherwise stated below; as depicted in Figure 1):

- 9. Patient demographics (age and sex on index date) (obtained directly from data source)
- 10. BMI, height, weight (most recent value on or before the index date) (obtained directly from data sources; BMI may be calculated if height and weight available)
- 11. Relevant comorbidities (obtained via ICD-10 codes), including:
 - 1. Weight-related comorbidities (i.e, type 2 diabetes, dyslipidaemia, hypertension)
 - 2. Neuropsychiatric conditions (mania, bipolar disorder, major depressive disorder [MDD], anorexia nervosa, bulimia)
 - 3. Uncontrolled hypertension, if possible
 - 4. Moderate or severe renal impairment
 - 5. End-stage renal disease
 - 6. Seizure disorder
 - 7. Hepatic impairment (defined by Child-Pugh score category, if available)
 - 8. Central nervous system tumour

- 12. History of, or current substance abuse/dependencies including acute opiate withdrawal (obtained via ICD-10 codes)
- 13. History of uncontrolled hypertension, seizures, bipolar disorder, MDD, anorexia nervosa, or bulimia (obtained via ICD-10 codes)
- 14. Prior medication use, including: naltrexone, bupropion, CYP2B6 inhibitors, CYP2B6 inducers, CYP2B6 substrates, CYP2D6 substrates, Monoamine oxidase inhibitors, Opioids, Opium alkaloids and derivatives and drugs that lower seizure threshold (obtained via ATC [Nordic data] or NDC [US data]) see Appendix 2 and 2A
- 15. Pregnancy status and breastfeeding status (obtained via ICD-10 codes)

All variables will be identified from the data sources outlined below using a pre-specified list of definitions per database (Appendix 3), to be defined in the SAP as final.

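### The label gives weight-related comorbidities as an open list; the study's baseline variable and code list close it to three conditions, so some overweight patients may be counted as off-label who are not

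*Protocol*

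**What the plan says.** The indication is worded openly wherever the protocol states it. Section 3 has "in the presence of at least one weight-related comorbidity (e.g., hypertension, type 2 diabetes mellitus, or dyslipidemia". Section 7, for the European approval, has "in the presence of one or more weight-related co-morbidities (e.g., type 2 diabetes, dyslipidaemia, or controlled hypertension". The rule for the non-adherent subgroup, near the end of Section 9.3.2, is also open: "having at least one weight-related co-morbidity (e.g., type 2 diabetes, controlled hypertension, or dyslipidemia) based on diagnostic codes". Note b to Figure 1 in Section 9.3.1, on baseline conditions, has "weight-related comorbidities (e.g., diabetes, dyslipidaemia".

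The study variables are worded as a closed list. Section 9.3.3 item 11, which defines baseline comorbidities, has "Weight-related comorbidities (i.e, type 2 diabetes, dyslipidaemia, hypertension". Section 9.3.2 item 3, which lists variables collected after the index date, has "Weight-related comorbidities (i.e., type 2 diabetes, dyslipidaemia, hypertension".

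Section 9.3.2 then ties the variables to codes: "All variables will be identified from the data sources via a pre-specified list of definitions (i.e., code lists; see Appendix 2". In Appendix 2 the rows that serve this purpose are diabetes (E10-E11), dyslipidaemia (E78) and hypertension (I10-I16). Appendix 3 likewise has rows for these three and no further weight-related condition.

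The variable is used in Section 8 and in Section 9.7.2, list (a) item 3. I read that item as weight management in a patient who meets neither the obesity arm nor the overweight-plus-comorbidity arm of the indication.

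**The concern.** For a patient with BMI 27 to <30, the comorbidity alone decides whether use is within the indication. If the label's list is open and the study's list is closed, a patient who qualifies through a fourth condition has no code by which to qualify and is counted under (a)3.

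That item feeds primary objective 2, the number and percentage of users compliant and non-compliant with the SmPC. It also feeds the AESI incidence by compliance group in Section 9.7.3.1. The study is meant to inform whether the SmPC should be revised, so use that may be on-label should not enter the off-label count unnoticed.

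**Working it through.** No sample-size or power figure is involved, so the check compares the passages.

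**1. Which list governs.** Section 7 places the focus on non-compliance at initiation, so the baseline list in 9.3.3 item 11 is the operative one. The list in 9.3.2 item 3 is post-index, but its wording is the same.

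**2. Open or closed.**

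| Place | Role | Form |
|---|---|---|
| Section 3 | indication | open (*e.g.*) |
| Section 7 | EU indication | open (*e.g.*) |
| 9.3.1, Figure 1 note b | baseline conditions | open (*e.g.*) |
| 9.3.2, non-adherence rule | compliance | open (*e.g.*) |
| 9.3.2 item 3 | post-index variable | closed (*i.e.*) |
| 9.3.3 item 11 | baseline variable | closed (*i.e.*) |
| Appendix 2 | codes | three conditions only |

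The concept is open in four places, closed in two, and closed in practice by the code list. Even if the open rule in 9.3.2 prevails, it is judged on diagnostic codes, and no code is supplied for a fourth condition. Appendix 3 does list non-fatal myocardial infarction and stroke, but 9.3.2 treats those as AESIs, not as qualifying conditions.

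**3. Direction.** Leaving out qualifying conditions can only move patients into (a)3. Two code rows work the other way. E10-E11 is wider than the type 2 diabetes that the rule names, and I10-I16 is not limited to the controlled hypertension that the rule names. Both can make an overweight patient look on-label. The net direction for the whole variable is therefore undetermined.

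**4. Who is affected.** Appendix 3 lists BMI as partly available in the US, and 9.3.2 makes provision for BMI being unavailable in the Nordic registries. Section 9.7.5 leaves BMI unimputed in the primary analysis and bars imputed values from this criterion. So the effect on (a)3 lies mainly in US patients with a recorded BMI. A patient who already fails on another ground, such as dose, the 16-week weight-loss rule or a contraindication, stays non-compliant either way. Only patients with no other failure change group in the compliant/non-compliant split.

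**5. Size.** Among patients with recorded BMI, let *f* be the share at 27 to <30, *n* the share of those with none of the three conditions, and *w* the share of those with another recorded weight-related condition. The share affected in (a)3 is *f × n × w*. The protocol gives none of the three. To show how far assumptions alone move the answer:

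- *f* = 5%, *n* = 20%, *w* = 10%: 0.05 × 0.20 × 0.10 = 0.001, or 0.1%.
- *f* = 20%, *n* = 40%, *w* = 40%: 0.20 × 0.40 × 0.40 = 0.032, or 3.2%.

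That is a 32-fold span (3.2 / 0.1). Assuming instead that 5% to 30% of the BMI band qualify only through an unlisted condition gives 0.05 × 0.05 = 0.25% to 0.20 × 0.30 = 6.0%. These are illustrations, not estimates.

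**The case against.** The strongest reply has four parts.

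- **The only spelled-out compliance rule is open, and (a)3 itself contains no list.** On this view the closure is inferred from a variable list and from absent code rows. That is correct as a description. But the variables are identified through those code rows, so an analyst who follows the plan has nothing with which to apply the open wording.
- **The SAP will settle it.** Section 9.3.3 says definitions per database become final there, and compliance is to be adapted to the local SmPC. This softens the point. It does not remove a contradiction that the protocol itself contains, and a SAP faithful to 9.3.3 and Appendix 2 would carry the closed list forward.
- **A closed list of the three conditions the label names is reproducible and defensible.** That stands, provided the protocol says the restriction is deliberate. It does not say so.
- **The issue is already visible.** Section 9.7.2 reports each component of non-adherence, so (a)3 appears separately. Section 9.4.1 also warns of misclassification of overweight with a comorbidity, though only for the Nordic data. Neither step separates overweight patients who have another weight-related condition from those who have none.

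A reader might go further and infer that cardiovascular and joint disease must count as qualifying, since Section 7 calls obesity and overweight "major risk factors for chronic diseases, including cardiovascular disease, orthopaedic/degenerative joint disease, and diabetes". That sentence is background on risk, not label text, and nothing in the protocol says either condition qualifies a patient.

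**Conclusion.** The inconsistency is real and minor. The indication and the non-adherence rule treat the three conditions as examples; the baseline variable and Appendix 2 treat them as the whole list. Followed as written, the plan counts a patient with known BMI 27 to <30 and only some other weight-related condition as outside the indication.

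Two stronger readings are not supported. One is that the non-compliance estimate is biased upwards overall: that holds for this omission alone, while the wide diabetes and hypertension codes push the other way. The other is a patient count obtained by applying assumed rates to the more than 20,000 US users expected in Section 9.4.2: every rate would be assumed, and the denominator ignores that BMI is only partly recorded and is not imputed for this criterion.

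The conclusion rests on my reading of (a)3 and on the label being open as the protocol quotes it. Whether any particular further condition is accepted under a local label cannot be settled from this document.

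**What to change.** 1. Use one definition in 9.3.2 (item 3 and the non-adherence rule), 9.3.3 item 11 and Appendix 2. Either add codes for the further conditions accepted under each local label, or state that the three-condition list is a deliberate operational restriction.
2. While doing so, reconcile the diabetes and hypertension code ranges with the conditions named in the rule.
3. In 9.7.2 (a)3, put patients with BMI 27 to <30 and none of the three conditions on their own line, split by whether another pre-specified weight-related condition is recorded.
4. Give the non-compliance percentage and the compliant/non-compliant AESI split with and without the patients who have such a condition.

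The cost is agreement on a short additional code list and one extra table line. Reporting both versions means the result does not hinge on which further conditions are chosen.
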